4.4. Sponsor Qualified Medical Personnel

The contact information for the sponsor's appropriately qualified medical personnel for the study is documented in the study contact list located in the Study Manual.

To facilitate access to appropriately-qualified medical personnel on study-related medical questions or problems, patients are provided with a contact card. The contact card contains,

at a minimum, protocol and investigational compound identifiers, patient study numbers, contact information for the investigational site, and contact details for a contact center in the event that the investigational site staff cannot be reached to provide advice on a medical question or problem originating from another healthcare professional not involved in the patient's participation in the study. The contact number can also be used by investigational staff if they are seeking advice on medical questions or problems; however it should be used only in the event that the established communication pathways between the investigational site and the study team are not available. It is therefore intended to augment, but not replace the established communication pathways between the investigational site and the study team for advice on medical questions or problems that may arise during the study. The contact number is not intended for use by the patient directly, and if a patient calls that number, he or she will be directed back to the investigational site.

5. STUDY TREATMENTS

For the purposes of this study, and per International Conference on Harmonisation (ICH) guidelines, investigational product is defined as a pharmaceutical form of an active ingredient or placebo being tested or used as a reference in a clinical trial, including a product with a marketing authorization when used or assembled (formulated or packaged) in a way different from the approved form, or when used for an unapproved indication, or when used to gain further information about an approved use (ICH E6 1.33).

For the purpose of this study, the investigational product is avelumab (MSB0010718C).

For the purpose of this study, "study treatment" refers to both the investigational product (avelumab) plus BSC and BSC alone administered to patients during participation in this study. Please see [Section 5.8](#) for additional information regarding BSC.

5.1. Allocation to Treatment

The investigator's knowledge of the treatment should not influence the decision to enroll a particular patient or affect the order in which patients are enrolled.

Qualified patients who have signed an Informed Consent Form and meet all eligibility criteria will be randomized in a 1:1 ratio to receive avelumab plus BSC (Arm A) or BSC alone (Arm B). Allocation of patients will be stratified according to best response to first-line chemotherapy (CR/PR vs. SD) and site of metastases (visceral vs. non-visceral) at the time of initiating first-line chemotherapy. The "non-visceral" stratum includes patients with locally-advanced disease as well as patients with only non-visceral disease. This stratified randomization will be centrally allocated across all centers using an Interactive Response Technology (IRT) system (an interactive web-based response system).

The site personnel (study coordinator or specified designee) will be required to enter or select information including but not limited to the user's identification (ID) and password, the protocol number, patient identifiers and demographic information, and stratification factors. The site personnel will then be provided with a treatment assignment. The IRT system will also provide a confirmation report containing the patient number; this confirmation report must be stored in the site's files.

Study treatment (Cycle 1 Day 1) must start within 3 days after patient randomization.

There is a 24-hour-a-day, 365-days-a-year IRT helpdesk available for any questions or issues. The study-specific IRT reference manual will provide the contact information and further details on the use of the IRT system.

Note: The IRT is the source of the patient number. The IRT system will provide the patient number at the end of the first IRT patient transaction.

Arm B patients who crossover to receive avelumab plus BSC will be assigned avelumab in the IRT system according to instructions provided by the Sponsor.

5.2. Patient Compliance with Avelumab Study Treatment

All doses of investigational product will be administered by the appropriately designated study staff at the investigational site.

5.3. Investigational Product Supplies

Avelumab (MSB0010718C) will be supplied for the study by Pfizer Global Clinical Supply, Worldwide Research and Development. Drug supplies will be shipped to the study sites with a Drug Shipment and Proof of Receipt form. This form will be completed, filed, and the shipment confirmed as directed on the bottom of the Drug Shipment and Proof of Receipt form. The investigator shall take responsibility for and shall take all steps to maintain appropriate records and ensure appropriate supply, storage, handling, distribution, and usage of investigational product in accordance with the protocol and any applicable laws and regulations.

5.3.1. Avelumab Dosage Form(s) and Packaging

Avelumab is a sterile, clear, and colorless solution intended for IV administration. Avelumab is formulated as a 20.0 mg/mL solution and will be supplied by the sponsor in single-use glass vials, stoppered with a rubber septum and sealed with an aluminum polypropylene flip-off seal.

Packaging and labeling will be in accordance with applicable local regulatory requirements and applicable Good Manufacturing Practice (GMP) guidelines. Avelumab will be packed in boxes each containing one vial. The information on the study treatment will be in accordance with approved submission documents.

Avelumab will be shipped in transport cool containers (2°C to 8°C) that are monitored with temperature monitoring devices.

5.3.2. Avelumab Preparation and Dispensing

See the Dosage and Administration Instructions (DAI), which is located in the Investigational Product Manual, for instructions on how to prepare the investigational product for administration. Investigational product should be prepared and dispensed by an appropriately qualified and experienced member of the study staff (eg, physician, nurse,

physician's assistant, practitioner, or pharmacist) as allowed by local, national, and institutional guidance.

Only qualified personnel who are familiar with procedures that minimize undue exposure to them and to the environment should undertake the preparation, handling, and safe disposal of anticancer agents.

Avelumab will be administered at the investigational site.

The contents of the avelumab vials are sterile and nonpyrogenic, and do not contain bacteriostatic preservatives. Any spills that occur should be cleaned up using the facility's standard cleanup procedures for biologic products.

For administration in this trial, avelumab drug product must be diluted with 0.9% sodium chloride (normal saline). Detailed information on infusion bags and medical devices to be used for the preparation of the dilutions and subsequent administration will be provided in the DAI. During avelumab administration, tubing with in-line, low protein binding 0.2 micron filter made with polyether sulfone (PES) must be used.

Avelumab must not be used for any purpose other than the trial. The administration of trial investigational product to patients who have not been enrolled into the trial is not covered by the trial insurance.

Any unused portion of the solution should be discarded in biohazard waste disposal with final disposal by accepted local and national standards of incineration.

5.4. Avelumab Administration

Avelumab will be administered at the investigational site on an outpatient basis as detailed in the DAI.

Avelumab will be administered at 10 mg/kg on Day 1 and Day 15 of each 4-week treatment cycle after all procedures/assessments have been completed as described in the [Schedule of Activities](#) table. All safety assessments must be performed, and results reviewed by the treating physician prior to study treatment administration.

Avelumab will be administered as a 1-hour IV infusion. In order to mitigate infusion-related reactions, premedication with an antihistamine and with paracetamol (acetaminophen) approximately 30 to 60 minutes prior to the first 4 infusions of avelumab is mandatory (for example, 25-50 mg diphenhydramine and 500-650 mg paracetamol [acetaminophen] IV or oral equivalent). Premedication should be administered for subsequent avelumab doses based upon clinical judgment and presence/severity of prior infusion reactions. The premedication regimen may be modified based on local treatment standards and guidelines, as appropriate, provided it does not include systemic corticosteroids. Sites should make every effort to target infusion timing to be as close to 1 hour as possible. However, given the variability of infusion pumps from site to site, time windows of -10 minutes and +20 minutes is permitted (ie, infusion time is 60 minutes: -10 min/+20 min). The exact duration of infusion should be recorded in both source documents and case report forms (CRFs).

Possible modifications of the infusion rate for the management of infusion-related reactions are described in [Section 5.4.3.2](#).

The dose amount required to prepare the avelumab infusion solution will be based on the patient's weight in kilograms (kg). All patients should be weighed within 3 days prior to dosing for every dose. If the patient experienced either a weight loss or gain >10% compared to the weight used for the last dose calculation, the amount of study drug required for preparation and administration for the current dose must be recalculated using this most recent weight obtained. For weight change less than 10%, the decision to recalculate the avelumab dose can be in accordance with institutional practice. Avelumab dose reduction for toxicity management is not permitted, however the next dose administration may be omitted due to persisting toxicity as described in [Table 3](#) and [Section 5.4.3](#).

5.4.1. Treatment after Initial Evidence of Radiologic Disease Progression

Immunotherapeutic agents such as avelumab may produce anti-tumor effects by potentiating endogenous cancer-specific immune responses. The response patterns seen with such an approach may extend beyond the typical time course of responses seen with cytotoxic agents, and can manifest as a clinical response after an initial increase in tumor burden or even the appearance of new lesions.

If radiologic imaging shows disease progression as assessed by BICR (or as assessed by Investigator as per Protocol Amendment 6, following the final OS update), after discussion between the Sponsor and Investigator, patients may continue to receive avelumab at the Investigator's discretion if the following criteria are met:

- Absence of clinical signs and symptoms (including worsening of laboratory values) of disease progression.
- No decline in ECOG performance status.
- Absence of rapid progression of disease by radiographic imaging.
- Absence of progressive tumor at critical anatomical sites (eg, cord compression) requiring urgent alternative medical intervention.

Patients who stop avelumab treatment, and then experience radiologic disease progression thereafter, will be eligible for re-treatment with avelumab at the discretion of the investigator and after discussion with the sponsor's medical monitor if 1) no cancer treatment was administered other than BSC since the last dose of avelumab, 2) the patient does not meet the safety withdrawal criteria, and 3) the trial is still open.

As per Protocol Amendment 6, following the final OS update, patients who stop avelumab treatment and subsequently experience radiologic disease progression, will no longer be eligible for re-treatment with avelumab.

5.4.2. Food Requirements

Avelumab may be administered without regard for food.

5.4.3. Recommended Dose Modifications

Every effort should be made to administer study treatment on the planned dose and schedule.

For avelumab, no dose modifications are permitted in this study, but next infusion may be omitted based on persisting toxicity. Recommended toxicity management guidelines with regard to avelumab infusion omissions are shown in Table 3.

Table 3. Avelumab Infusion Omissions for Avelumab Product-Related Toxicity

| Toxicity | NCI CTCAE Severity Grade | Avelumab |
|---|--------------------------|---|
| | | Treatment Modification |
| Infusion-related Reaction / Hypersensitivity | Grade 1-4 | 
 See Section 5.4.3.2 and Table 4. |
| Tumor lysis syndrome | Grade 1-4 | 
 See Section 5.4.3.3 and Figure 2. |
| Immune-related AE (irAE) | Grade 1-4 | 
 See Section 5.4.3.4 and Table 5. |
| Drug-related adverse reactions (excluding infusion-related reaction / hypersensitivity and immune-related AE) | Grade 1 | 
 Continue as per schedule. |
| | Grade 2 | 
 Continue as per schedule. |
| | Grade 3 | 
 Withhold until recovery to Grade \leq1 or baseline. Permanently discontinue if toxicities do not resolve to Grade \leq1 or baseline within 12 weeks of last administration or if the same Grade 3 toxicity recurs. 
Exceptions are:
 
 Laboratory values out of normal range that do not have any clinical correlate. |
| | Grade 4 | 
 Permanently discontinue. 
Exceptions are:
 
 Laboratory values out of normal range that do not have any clinical correlate. |

Avelumab infusion-related reactions (including hypersensitivity) and irAEs should be handled according to guidelines in [Section 5.4.3.2](#) Management of Avelumab Infusion-Related Reactions and [Section 5.4.3.4](#) Management of Avelumab Immune-Related Adverse Events.

5.4.3.1. Special Precautions for Avelumab Administration

In order to mitigate avelumab infusion-related reactions, premedication with an antihistamine and with paracetamol (acetaminophen) approximately 30 to 60 minutes prior to the first 4 infusions of avelumab is mandatory (for example, 25-50 mg diphenhydramine and 500-650 mg paracetamol [acetaminophen] IV or oral equivalent). Premedication should be

administered for subsequent avelumab doses based upon clinical judgement and presence/severity of prior infusion reactions. The premedication regimen may be modified based on local treatment standards and guidelines, as appropriate, provided it does not include systemic corticosteroids.

As with all monoclonal antibody therapies, there is a risk of allergic reactions including anaphylactic shock. Avelumab should be administered in a setting that allows for immediate access to an intensive care unit or equivalent environment and administration of therapy for anaphylaxis, such as the ability to implement immediate resuscitation measures. Steroids (dexamethasone 10 mg), epinephrine (1:1,000 dilution), allergy medications (IV antihistamines), bronchodilators, or equivalents, and oxygen should be available for immediate access.

Infusion of avelumab will be stopped in case of Grade ≥ 2 infusion-related, allergic, or anaphylactic reactions. Symptoms of avelumab infusion related reactions include, but are not limited to, fever, chills, flushing, hypotension, dyspnea, wheezing, back pain, abdominal pain, and urticaria. Management of avelumab infusion related reactions is described in Section 5.4.3.2. Patients should be instructed to immediately report to the Investigator any delayed reactions that may occur after they leave the clinic.

5.4.3.2. Management of Avelumab Infusion-Related Reactions/Hypersensitivity Reactions

Since avelumab is administered IV, infusion-related reactions may occur (with symptoms such as fever, chills, rigors, diaphoresis, and headache). Treatment of the infusion-related reaction and modifications of avelumab infusion are mainly dependent upon severity, as indicated in Table 4.

Table 4. Treatment Modification for Symptoms of Avelumab Infusion-Related Reactions

| NCI CTCAE Grade | Treatment Modification for Avelumab |
|--|--|
| Grade 1 – mild 
Mild transient reaction; infusion interruption not indicated; intervention not indicated. | 
Decrease the avelumab infusion rate by 50%* and monitor closely for any worsening. |
| Grade 2 – moderate 
Therapy or infusion interruption indicated but responds promptly to symptomatic treatment (eg, antihistamines, NSAIDs, narcotics, IV fluids); prophylactic medications indicated for ≤ 24 hours. | 
Temporarily discontinue avelumab infusion.Resume infusion at 50% of previous rate* once infusion-related reaction has resolved or decreased to at least Grade 1 in severity. Monitor closely for any recurrence or worsening. |
| Grade 3 or Grade 4 – severe or life-threatening 
Grade 3: Prolonged (eg, not rapidly responsive to symptomatic medication and/or brief interruption of infusion); recurrence of symptoms following initial improvement; hospitalization indicated for clinical sequelae. | 
Stop the avelumab infusion immediately and disconnect infusion bag and tubing from the patient.Subjects have to be withdrawn immediately from avelumab treatment and must not receive any further avelumab treatment. |

Table 4. Treatment Modification for Symptoms of Avelumab Infusion-Related Reactions

| NCI CTCAE Grade | Treatment Modification for Avelumab |
|--|-------------------------------------|
| 
Grade 4: Life-threatening consequences; urgent intervention indicated. | |

IV=intravenous, NCI-CTCAE=National Cancer Institute Common Terminology Criteria for Adverse Events, NSAIDs=nonsteroidal anti-inflammatory drugs.

[figure not shown]
*If the avelumab infusion rate has been decreased by 50% due to an infusion reaction, it must remain decreased for the next scheduled infusion. If no infusion reaction is observed at the next scheduled infusion, at the Investigator's discretion, the infusion rate may be returned to baseline at subsequent infusions.

Additional Modifications for Patients with Grade 2 Infusion-Related Reactions: In the event of a Grade 2 infusion-related reaction that does not improve or worsens after implementation of the modifications indicated in [Table 4](#) (including reducing the infusion rate by 50%), the investigator may consider treatment with corticosteroids, and the infusion should not be resumed for that dose. At the next dose, the investigator may consider the addition of H2-blocker antihistamines (eg, famotidine or ranitidine), meperidine, or ibuprofen to the mandatory premedication. Prophylactic steroids are NOT permitted.

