Immune-related Adverse Events: As of 01 June 2015, a cumulative review identified 106 patients with potential immune-related adverse events (irAEs) out of 717 patients (14.8%) treated in the pooled expansion cohort of trial EMR 100070-001. Treatment-related potential irAEs were observed in 71 of the 717 patients (9.9%). Hypothyroidism was the most frequent treatment-related irAE, which occurred in 32 patients (4.5%) in the pooled expansion cohort. The other frequent irAEs, which were considered as treatment-related, were pneumonitis (8 patients; 1.1%), autoimmune hepatitis and hyperthyroidism (4 patients; 0.6%), and colitis and dry eye (3 patients each; 0.4%). Additional treatment-related irAEs were seen in 2 or 1 patients in the pooled expansion cohort.

Infusion-Related Reactions: Two suspected unexpected serious adverse reactions (SUSARs; anaphylactic reaction and infusion-related reaction) involving 2 patients were reported in December 2013 and triggered a cumulative review of serious and non-serious cases of infusion-related reactions and hypersensitivity across the avelumab program. Following evaluation of safety signals, infusion-related reactions and hypersensitivity were classified as a newly identified risk (previously classified as a potential risk) and a mandatory premedication regimen of a histamine H1 receptor (H1) blocker plus acetaminophen/paracetamol was implemented for all trial patients starting 29 January 2014.

As of 01 June 2015, 138 of 717 patients (19.2%) in the pooled expansion cohort experienced at least 1 episode of infusion-related reaction. Most of the events were Grade 1 (30 patients, 4.2%) or Grade 2 (101 patients, 14.1%) in intensity, and Grade 3 (5 patients, 0.7%) or Grade 4 events (2 patients, 0.3%) were less frequent. No Grade 5 events were reported. Most of the infusion-related reactions had an onset after the first (91 patients, 12.7%) or second (35 patients, 4.9%) avelumab infusion, and those with an onset after the third (9 patients, 1.3%) or fourth avelumab infusion (3 patients, 0.4%) were less frequent. In 17 patients (2.4%), avelumab treatment was discontinued because of infusion-related reaction.

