1.6. Patient Discontinuation

- Required in-clinic visits, including Avelumab administrations, may be missed without causing discontinuation from the maintenance treatment phase of the study. However, all study patient withdrawal criteria listed in Protocol [Section 6.5](#) remain applicable.
- For study patient discontinuation reporting in the CRF: select the most appropriate status for discontinuation; if the discontinuation is associated with the current COVID-19 pandemic, enter “COVID-19” in the “Specify Status” field.

- It's important to continue to enter the CRF data as quickly as possible, so we have access to the data for safety monitoring. If the sponsor determines that the impact of COVID-19 on protocol visits and procedures and associated timeframes needs to be reported on a case report form (CRF), this will be requested.

17. SUPPLEMENT 1: CROSSOVER FROM BSC ALONE (ARM B) TO AVELUMAB PLUS BEST SUPPORTIVE CARE

This supplement provides details for patients in the BSC alone arm who crossover to receive avelumab plus BSC. All other information in the protocol not addressed in this supplement still apply. After 60 days following the final OS update or approval of Amendment 6, whichever is later, no additional Arm B patients will be allowed to crossover to avelumab plus BSC.

ELIGIBILITY CRITERIA

Inclusion Criteria

Patients randomized to Arm B must meet all of the following inclusion criteria to be eligible to crossover from BSC alone to avelumab plus BSC:

1. Patients randomized to Arm B (BSC alone) ongoing in the maintenance phase (ie, patients must not have completed the EOT visit).
2. Patients without progressive disease while on study as per RECIST v1.1 guidelines as assessed by the investigator.
3. Evidence of a signed and dated informed consent document indicating that the patient (or a legally acceptable representative, as allowed by local guideline/practice) has been informed of the aspects of crossover.
4. Patients who are willing and able to comply with scheduled visits, treatment plans, laboratory tests, and other study procedures.
5. Eastern Cooperative Oncology Group (ECOG) performance status (PS) 0 or 1 ([Appendix 1](#)).
6. Adequate bone marrow function, including:
 - a. Absolute neutrophil count (ANC) $\geq 1,500/\text{mm}^3$ or $\geq 1.5 \times 10^9/\text{L}$;
 - b. Platelets $\geq 100,000/\text{mm}^3$ or $\geq 100 \times 10^9/\text{L}$;
 - c. Hemoglobin ≥ 9 g/dL (may have been transfused).

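### The next-dose advice for a Grade 2 infusion reaction that fails first measures overlaps Table 4's Grade 3 definition, which bars further avelumab

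*Protocol*

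**What the plan says.** Table 4 in Protocol Section 5.4.3.2 grades infusion-related reactions and ties an action to each grade.

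- **Grade 2, definition:** "Therapy or infusion interruption indicated but responds promptly to symptomatic treatment". **Action:** interrupt the infusion, restart at half the previous rate only after the reaction has resolved or fallen to Grade 1, and watch for recurrence or worsening.
- **Grade 3, definition:** "Prolonged (eg, not rapidly responsive to symptomatic medication and/or brief interruption of infusion); recurrence of symptoms following initial improvement", or a need for hospitalization because of sequelae. Grade 4 is a life-threatening reaction.
- **Grade 3 or 4, action:** stop at once. "Subjects have to be withdrawn immediately from avelumab treatment and must not receive any further avelumab treatment".

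The paragraph after the table, on additional modifications for Grade 2 reactions, begins: "In the event of a Grade 2 infusion-related reaction that does not improve or worsens after implementation of the modifications indicated in" Table 4. It counts the halved rate among the measures that have failed. Corticosteroids may be considered and that day's infusion is not resumed. It continues: "At the next dose, the investigator may consider the addition of H2-blocker antihistamines", and lists other optional premedication.

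For infusion-related reactions of any grade, Table 3 in Section 5.4.3 says only "See Section 5.4.3.2 and Table 4".

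**The concern.** The paragraph is triggered by a reaction failing to improve, or getting worse, after the first measures. That is close to how Table 4 describes Grade 3. The two texts then lead to opposite actions: the paragraph foresees another dose and the table forbids one. The paragraph neither asks the investigator to regrade the reaction nor limits the next-dose advice to reactions that are still Grade 2.

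The boundary matters because the protocol treats Grade 3 as its line for withholding avelumab. Known Grade 3 or higher hypersensitivity to monoclonal antibodies is an exclusion at entry (Section 4.2, criterion 12) and again at crossover (Supplement 1, exclusion 6).

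Patients starting avelumab are the most exposed, since most Phase 1 reactions began with the first or second infusion. Under Amendment 6 these are Arm B patients crossing over, to whom Supplement 1 applies the Arm A treatment rules.

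**Working it through.** The plan gives no figure to reproduce on this point. The main check sets the paragraph against Table 4, case by case.

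**Cases that meet the Grade 3 wording**

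1. *No improvement after the infusion is interrupted.* This fits lack of rapid response to brief interruption. If symptomatic medication was also given without prompt effect, the Grade 2 condition fails as well.
2. *Symptoms return or worsen after the half-rate restart.* Table 4 allows that restart only after resolution or a fall to Grade 1. A patient who reached it by following the table had therefore already improved, and a return of symptoms is recurrence after initial improvement.
3. *Worsening until hospitalization or urgent intervention is needed.* This is Grade 3 or 4 by definition.

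In all three cases Table 4 requires permanent withdrawal, while the paragraph goes on to the next dose.

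**Cases that can stay at Grade 2**

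4. *Residual Grade 1 symptoms that persist, or rise modestly, at the half rate.*
5. *A reaction that interruption alone does not control but that then responds promptly to medication.* This one is arguable, because the Grade 3 wording joins medication and interruption with and/or.

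The paragraph does not separate cases 1 to 3 from cases 4 and 5.

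**Does other text settle it?** Table 3 points to the section and the table without an order of precedence. Section 5.4.3.1 says only that the infusion is stopped at Grade 2 or higher. By contrast, Table 5 states escalation rules outright: worsening rash, and persistent or recurrent Grade 2 diarrhea or colitis, are to be managed at the higher grade. The infusion-reaction paragraph has no equivalent.

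**Outer bound on size.** Inputs are from the Phase 1 pooled expansion cohort in Section 1.2.2.1 (717 patients): "Most of the events were Grade 1 (30 patients, 4.2%) or Grade 2 (101 patients, 14.1%) in intensity", with 5 patients at Grade 3 and 2 at Grade 4.

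- All reactions: 30 + 101 + 5 + 2 = 138.
- Grade 2 or higher: 101 + 5 + 2 = 108, and 108/717 = 15.06% (exact Clopper-Pearson 95% CI 12.5% to 17.9%).
- Onset after infusion 1 or 2: (91 + 35)/138 = 126/138 = 91.3%.

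The documents do not give the share of reactions that fail first measures. With assumed shares, per 100 patients starting avelumab:

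| Assumed share failing first measures | Calculation | Per 100 |
|---|---|---|
| 5% | 0.05 × 15.06 | 0.75 |
| 10% | 0.10 × 15.06 | 1.51 |
| 20% | 0.20 × 15.06 | 3.01 |
| 100% (bound) | 1.00 × 15.06 | 15.06 |

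Only part of each figure would meet the Grade 3 wording.

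**The case against.** The best defence is that the texts can be read together. Section 5.4.3.2 opens by saying that management depends mainly on severity as set out in Table 4, and Table 4 sits inside that section, so Table 3 is not pointing to two rival sources. The Grade 3 bar is mandatory, whereas the paragraph is headed Grade 2 and is largely permissive. Its one firm step, not resuming that day's infusion, is protective. The Grade 2 label may describe the grade at onset. The Grade 2 action column lists no medication, so failing those measures is not the same as failing symptomatic treatment.

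Practice may also be cautious. In Phase 1, 17 patients stopped avelumab for infusion reactions but only 5 + 2 = 7 had Grade 3 or 4. At least 17 − 7 = 10 therefore stopped with a worst grade of 2 or lower, although the stopping rules used there are not shown.

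Some of this stands. The paragraph has a coherent scope in cases 4 and 5, it does not order re-dosing, and a careful investigator would probably regrade. The defence does not remove the overlap. The word mainly sets no precedence, and the paragraph keeps the Grade 2 label on reactions whose described course matches Grade 3. An onset-grade reading makes matters worse, because next-dose advice would then follow a reaction that has since become Grade 3. The range of 0.75 to 3.01 per 100 rests on assumed shares and does not measure the defect.

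**Conclusion.** The concern holds as a minor patient-safety point. For several reaction courses the protocol states two rules with opposite actions, next-dose advice and permanent withdrawal, and does not say which applies. This rests on reading the definitions. It says nothing about how often each course occurs.

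The number of patients affected cannot be computed: the share of reactions failing first measures, the share of those meeting the Grade 3 wording, and the number crossing over are all missing. The outer bound of about 15 per 100 patients starting avelumab assumes that the Phase 1 rate carries over. It also counts reactions that settled promptly and those that were already Grade 3 or 4.

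Exposure is limited in time. Supplement 1 sets a closing date, 60 days after the later of Amendment 6 approval and the final OS update, beyond which "no additional Arm B patients will be allowed to crossover to avelumab plus BSC".

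No efficacy analysis is affected. The SAP is based on protocol amendment 4 and has no crossover provision, so any inconsistent grading in its infusion-reaction tables (SAP Section 6.6.4) concerns randomized Arm A only.

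**What to change.** Add one sentence to the paragraph in Section 5.4.3.2: *A reaction that meets the Table 4 Grade 3 definition after these measures is graded and managed as Grade 3, with permanent withdrawal of avelumab.* Then limit the premedication advice for the following infusion to reactions that remain Grade 2. This follows the escalation convention already used in Table 5.

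The cost is one sentence, one limiting phrase and a clarification letter to sites, with no new data collection. A few patients who would otherwise have been re-dosed may lose further avelumab, which is what Table 4 already requires for them.
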